5.2 Treatments

The test article consists of one 3mL bottle of SCH1 ophthalmic suspension. Doses will be administered directly from the bottle. See section 8.0 for storage, handling and administration. The placebo, which consists of the vehicle for SCH1, will be supplied in an identical 3mL bottle the placebo will.

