2.5 Dose Rationale

Each drop of SCH1 (approx. 80-110 microliters) contains 0.2% chlorhexidine gluconate and 1% prednisolone acetate. To adequately treat both the inflammatory and infectious components of acute conjunctivitis, frequent dosing is employed early in the course of infection which can be tapered rapidly as symptoms resolve. We will employ a regimen of 1 drop every two hours while awake in affected eyes on Day 1 followed by 1 drop four times a day for the remaining four days of treatment.

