4.3 Analysis Unit

The primary analysis will be performed on one eye of each subject. If both eyes qualify, the eye with the worse grade will be designated as the study eye. If both eyes have equal grade, the eye with more recent onset of symptoms will be designated as the study eye. If both eyes experienced onset of symptoms at the same time, the right eye will be designated as the study eye.

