6.0 Selection and Withdrawal of Subjects

6.1 Inclusion Criteria

Subjects must meet all of the following criteria to be included in the study:

- A documented history of symptoms consistent with infectious conjunctivitis
- Onset of symptoms in most recently affected eye less than 72 hours prior to visit
- At least 18 years of age
- Women of childbearing age must have a negative urine pregnancy test prior to starting the study drug and must not be lactating.
- Female subjects of non-childbearing potential must meet at least one of the following criteria:
 1. Premenarche females, defines as:
 - a. Females who have not had onset of menstrual cycle
 2. Postmenopausal females, defined as:
 - a. Females over 60
 - b. Females between 45 and 60 of age who are amenorrheic for at least 2 years
 3. Females who have had a hysterectomy and/or bilateral oophrectomy.All other female subjects will be considered to be of childbearing potential.
- Subjects or their guardians must be capable of understanding the purpose and risks of the study; able to give informed consent (and assent by pediatric subjects, if required) and to comply with the study requirements

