6.2 Exclusion Criteria

Subjects with any of the following will be excluded from the study:

- Conjunctivitis in which the most recently affected eyes had onset of symptoms greater than 72 hours prior to visit
- History of chronic allergic conjunctivitis, including vernal or atopic keratoconjunctivitis
- Presence of corneal ulcer, endophthalmitis, or other confounding ocular infectious process
- Active herpes virus ocular infection

- Patient with ocular conditions potentially interfering with conjunctival or corneal grading (e.g. chronic conjunctival injection after multiple surgeries, pseudophakia, or bullous keratopathy, etc.)
- Known steroid-responder (steroid-response glaucoma)
- Patient taking topical anti-inflammatory drops on a chronic basis
- Pregnant women
- Any current or history of substance abuse, psychiatric disorder or a condition that, in the opinion of the investigator, may invalidate communication or compliance with the protocol or return to study visits
- Known allergy to chlorhexidine gluconate or prednisolone acetate

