8.2 Study Drug Administration

The study drug is administered as one drop to the affected eye every two hours while awake on Day 1, four times per day while awake for Day 2 through Day 5. The drugs are administered by the patient.

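### The protocol does not settle whether a second affected eye is dosed; if it is, with about 8 Day 1 doses per eye, the single 3 mL bottle is too small

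*Combined protocol and SAP*

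**What the plan says.** Section 5.2 supplies a single bottle ("The test article consists of one 3mL bottle of SCH1 ophthalmic suspension") and an identical 3 mL bottle of vehicle for placebo. For how to give it, 5.2 sends the reader on: "See section 8.0 for storage, handling and administration". Section 7.2 lists dispensing at Visit 1 only, and no section mentions a second bottle or resupply.

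The two dosing statements differ on the eye:

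- Section 2.5: "1 drop every two hours while awake in affected eyes on Day 1 followed by 1 drop four times a day", the latter for the other four days.
- Section 8.2: "one drop to the affected eye every two hours while awake on Day 1", then four times a day on Days 2 to 5.

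Section 2.5 also gives the drop volume: "Each drop of SCH1 (approx. 80-110 microliters".

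Section 4.3 foresees bilateral disease: "If both eyes qualify, the eye with the worse grade will be designated as the study eye". It chooses the eye to be analysed and does not say whether the other eye is treated.

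**The concern.** A patient with two affected eyes could be told to treat both (2.5) or one (8.2). The grammatical number does not decide it, because the protocol uses singular and plural for the same onset criterion: "Onset of symptoms in most recently affected eye less than 72 hours prior to visit" in 6.1 and "Conjunctivitis in which the most recently affected eyes had onset of symptoms greater than 72 hours prior to visit" in 6.2.

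The choice matters because the supply is fixed. One bottle serves one eye comfortably. If it has to serve two, it may run out before the course ends and, in some cases, before the Day 5 assessment. The study eye would then have gone untreated for part of the period over which the primary endpoint is judged. The compliance checks in 8.3 might not show this clearly: in the return log, a bottle emptied early looks much like one used up on schedule, and only the patient's own dosing record would separate them.

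**Working it through.** The documents give no derivation of the 3 mL, so there is no stated calculation to reproduce. The check compares the stated volume with the stated regimen.

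**Inputs from the protocol.** Supply 3 mL (5.2). Drop volume about 80-110 microlitres (2.5). One drop per dose. Days 2-5: 4 × 4 = 16 doses per eye (2.5, 8.2). Primary assessment at Visit 3, Day 5, ±1 day (7.2).

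**Assumptions.** All 3 mL is usable, with no overfill and no wasted drops. Both eyes are dosed from Day 1. The number of Day 1 doses per eye, k, is not stated: 16 waking hours at two-hour intervals gives 8 or 9. That is an upper-end figure, because dosing starts only after the screening visit.

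**One eye.** Need = (k + 16) × drop volume. At the extreme, (9 + 16) × 0.110 = 2.75 mL, which fits in 3 mL.

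**Two eyes.** Full course: 2 × (k + 16) drops. Through Day 4, which is the least needed before a Day 5 visit (no Day 5 dose yet taken): 2 × (k + 12) drops.

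| k | Full course, drops | mL at 80-110 | Through Day 4, drops | mL at 80-110 | Largest drop lasting through Day 4 (microlitres) |
|---|---|---|---|---|---|
| 3 | 38 | 3.04-4.18 | 30 | 2.40-3.30 | 100 |
| 4 | 40 | 3.20-4.40 | 32 | 2.56-3.52 | 93.75 |
| 6 | 44 | 3.52-4.84 | 36 | 2.88-3.96 | 83.3 |
| 8 | 48 | 3.84-5.28 | 40 | 3.20-4.40 | 75 |
| 9 | 50 | 4.00-5.50 | 42 | 3.36-4.62 | 71.4 |

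The last column is 3000 divided by the drops needed through Day 4.

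**Capacity of the bottle.** 3/0.080 = 37.5, so 37 drops; 3/0.095 = 31.6, so 31; 3/0.110 = 27.3, so 27. Setting 2 × (k + 12) at or below these, one bottle lasts through Day 4 for k up to 6 at 80 microlitres, 3 at 95 and 1 at 110.

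**Doses missed at k = 8.** The bottle gives 18, 15 or 13 complete two-eye doses at 80, 95 or 110 microlitres, with one odd drop left. Of 24 doses per eye over the full course, 5-6, 8-9 or 10-11 are missed. Of the 20 due by the end of Day 4, 1-2, 4-5 or 6-7 are missed.

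**Sensitivity to fill, at 80 microlitres.** For k = 3 and 4 the full-course shortage is 0.04 and 0.20 mL, removed by 1.3% and 6.7% overfill. For k = 8 it is 0.84 mL, needing 28%. The k = 8 need through Day 4 (3.20 mL) would be met by an assumed 10% overfill (3.3 mL, 41 drops against 40). At 110 microlitres even 20% overfill (3.6 mL, 32 drops) does not meet the full-course need at k = 1 (34 drops).

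**Sensitivity to the visit window, at k = 8.** If Visit 3 falls on Day 4 before that day's doses, the need is 2 × (8 + 8) = 32 drops, or 2.56-3.52 mL, short only above about 94 microlitres.

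**The case against.** The strongest reply is that nothing has been miscalculated. Section 5.2 points to section 8 for administration, 8.2 speaks of one eye, and on that reading 3 mL is enough at every stated drop size. This stands: a reader might infer that the bottle was wrongly sized, but the documents contain no calculation linking 3 mL to a number of doses, and the shortage exists only if both eyes are dosed. What remains is that 2.5 read plainly doses both eyes, and the stated supply then does not deliver the stated regimen at about 8 Day 1 doses.

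A reader might also infer that the bottle fails from 3 Day 1 doses upward. On nominal figures it does, but by 0.04 mL at 80 microlitres, with an approximate drop size (break-even 78.9 microlitres) and an unstated fill. At 3 doses the bottle still lasts through Day 4 at 80 and 95 microlitres. The documents do not support a firm threshold there, nor a shortage before the Day 5 assessment across the whole drop range.

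Finally, section 4.3 is a conditional rule and gives no frequency of bilateral disease. The consent document, which section 15.0 describes as attached, was not available here and may carry dosing instructions. Both points are fair. Neither removes the difference between 2.5 and 8.2.

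**Conclusion.** The protocol leaves open whether a second affected eye is treated. If it is, and patients take about 8 Day 1 doses per eye, one 3 mL bottle is short across the stated drop range, both for the full course (by 0.84-2.28 mL) and through Day 4 (by 0.20-1.40 mL). With 3-4 Day 1 doses the shortage at 80 microlitres is marginal, falls only on Day 5 and would be removed by modest overfill. A shortage before Day 5 then needs drops above about 100 microlitres (3 doses) or about 94 (4 doses). If one eye is treated there is no shortage.

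This rests on 3 mL usable, both eyes dosed from Day 1, no wasted drops and an assumed 16-hour waking day.

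A reader might infer that the comparison itself is compromised. The documents do not support that: both arms receive the same volume, so there is no supply imbalance and no push towards a false positive. The likely direction is some dilution of the effect among bilateral patients. Its size cannot be stated, because neither the share of such patients nor the response to a shortened course is given. The point is minor.

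**What to change.** State in 2.5 and 8.2, in the same words, which eyes are dosed.

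- **If all affected eyes are dosed:** amend 5.2 and the Visit 1 dispensing step in 7.2 so that patients with both eyes affected at Visit 1 receive two identical masked 3 mL bottles under the same patient number, in both arms. The 6 mL covers the 5.50 mL maximum (50 drops × 0.110 mL). The second bottle depends only on baseline eye status, so it does not reveal the arm.
- **If only the study eye is dosed:** say so and keep one bottle.

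The dose, the schedule and the study-eye analysis in 4.3 do not change. The cost is a few sentences plus, under the first option, one extra bottle per bilateral patient: at most about 30 for the roughly 30 subjects in section 5.0.

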5.3 Duration

Enrollment for the study is expected to require twelve months. Patients will be followed for five days.

6.0 Selection and Withdrawal of Subjects

6.1 Inclusion Criteria

Subjects must meet all of the following criteria to be included in the study:

- A documented history of symptoms consistent with infectious conjunctivitis
- Onset of symptoms in most recently affected eye less than 72 hours prior to visit
- At least 18 years of age
- Women of childbearing age must have a negative urine pregnancy test prior to starting the study drug and must not be lactating.
- Female subjects of non-childbearing potential must meet at least one of the following criteria:
 1. Premenarche females, defines as:
 - a. Females who have not had onset of menstrual cycle
 2. Postmenopausal females, defined as:
 - a. Females over 60
 - b. Females between 45 and 60 of age who are amenorrheic for at least 2 years
 3. Females who have had a hysterectomy and/or bilateral oophrectomy.All other female subjects will be considered to be of childbearing potential.
- Subjects or their guardians must be capable of understanding the purpose and risks of the study; able to give informed consent (and assent by pediatric subjects, if required) and to comply with the study requirements

6.2 Exclusion Criteria

Subjects with any of the following will be excluded from the study:

- Conjunctivitis in which the most recently affected eyes had onset of symptoms greater than 72 hours prior to visit
- History of chronic allergic conjunctivitis, including vernal or atopic keratoconjunctivitis
- Presence of corneal ulcer, endophthalmitis, or other confounding ocular infectious process
- Active herpes virus ocular infection

- Patient with ocular conditions potentially interfering with conjunctival or corneal grading (e.g. chronic conjunctival injection after multiple surgeries, pseudophakia, or bullous keratopathy, etc.)
- Known steroid-responder (steroid-response glaucoma)
- Patient taking topical anti-inflammatory drops on a chronic basis
- Pregnant women
- Any current or history of substance abuse, psychiatric disorder or a condition that, in the opinion of the investigator, may invalidate communication or compliance with the protocol or return to study visits
- Known allergy to chlorhexidine gluconate or prednisolone acetate

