Eligibility Criteria	
Inclusion Criteria
 
 • Conjunctivitis (as defined below) within 72 hours of initial ocular symptoms. • At least 18 years of age. • Subjects capable of understanding the purpose and risks of the study, and able to give informed consent. • Conjunctivitis diagnosis defined as presence of the two cardinal signs of acute conjunctivitis- 1) bulbar conjunctival injection and 2) conjunctival discharge/exudates. • A three-point rating scale (0=absent, 1=mild, 2=moderate, 3=severe) will be employed to grade conjunctival discharge/exudates. • All patients will require a rating of 1(mild) or greater for conjunctival discharge/exudates. • Patients will require a rating of 1 (mild) for bulbar conjunctival injection.
	
Exclusion Criteria
 
 • Conjunctivitis greater than 72 hours after initial ocular symptoms • Corneal ulcer, endophthalmitis, or any other confounding infection of the eye • Patients taking topical anti-inflammatory medications on a chronic basis • Known steroid glaucoma responders • Active herpes ocular infection • Pregnant women • Known allergy to chlorhexidine
Trial Design	This is a phase II single-center, prospective, placebo-controlled, randomized study of SCH1 in the treatment of acute infectious conjunctivitis. Study drug will be evaluated against vehicle.
Primary Endpoint	Clinical cure defined as rating of 0/3 for bulbar conjunctival injection and 0/3 for conjunctival exudates/discharge or clinical success defined as an overall decrease by 3 in the sum of both grades.

Secondary	
 Patients will keep a self log of symptom score each of the 5 days of the study
Number of Subjects	
 30 (15 per treatment arm)
Target Population	
 Patients with infectious conjunctivitis defined by bulbar conjunctival injection (rated at least 1 on 3 point grading scale) and conjunctival exudates / discharge (rated at least 1 on 3 point grading scale). Patients greater than one year of age. Patients of any race or ethnic group.
Length of Study	
Enrollment period: 12 months Treatment period: 5 days Overall duration: 6 months 5 days

Study Drug	
Subjects will be randomized to one of the following treatment arms: Treatment Arm A: SCH1 Treatment Arm B: Placebo (Vehicle only)

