2.3 SCH1

SCH1 is a novel combination anti-infective / steroid eye drop with *in vitro* efficacy against many bacteria, yeasts, fungi and human adenovirus. The product contains two FDA-approved active pharmaceutical ingredients (Pred Forte, or prednisolone acetate 1%, application #017011, approved May 30, 1973; chlorhexidine gluconate, approved December 28, 1995). The combination is formulated as a 0.2% chlorhexidine 1% prednisolone acetate ophthalmic suspension. In preclinical evaluation, it demonstrated antimicrobial efficacy on contact with ocular isolates of *S.aureus*, *P. aeruginosa*, *E. coli*, *C. albicans*, and *A. brasiliensis*. A review of preclinical studies is provided in the investigators brochure.

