6.3 Subject Withdrawal Criteria

Subjects will be removed from the study for the following reasons:

- Subjects meet criteria for rescue (see section 6.4)
- Subjects withdrawal of consent
- Investigator decides it is in best interest of subject to withdraw from the study due to safety or efficacy issues
- Subject lost to follow up
- Study discontinuation by JD
-

An excessive rate of withdrawals can render the study uninterpretable: therefore unnecessary withdrawal of subjects should be avoided. A subject who withdraws for any reason should be encouraged to return to have the End of Treatment assessments performed. If a subject is lost to follow-up at any point during the study, attempts to contact the subject should be documented, and Subjective Symptoms Score should also be obtained. The reason for withdrawal from the study must be documented in the CRF by the Investigator.

If the subject withdraws from the trial and also withdraws consent for disclosure of future information, no further evaluation should be performed and no additional data should be collected. JD or DR may retain and continue to use any data collected before such withdrawal of consent.

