6.4 Subject Rescue Criteria and Procedures

Subjects who experience onset of a corneal infiltrate, intraocular inflammation, or glaucoma are to receive rescue therapy. Dosing with SCH1/placebo is to be stopped at the time of administration of rescue therapy. All evaluations scheduled for visit 3/End of Treatment should be performed at this time.

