7.0 Treatment of Subjects

Subjects meeting all the inclusion criteria and none of the exclusion criteria will be accepted into the study. Each subject must read and sign an informed consent form (or assent provided for pediatric subjects) prior to any screening procedures being performed. Subjects will be randomized either to placebo or SCH1, and will be followed in an outpatient setting. After their initial visit, subjects will come to the study center on day 3 and Day 5. Safety and efficacy measurements will be taken on these visits.

Potential risks and benefits to subjects participating in this study are detailed in the Subject Informed Consent Form.

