10.6 Adverse Events

10.6.1 Definition of Adverse Events

An adverse event is defined as any untoward medical occurrence in a patient or clinical investigation subject administered a pharmaceutical product and which does not necessarily have a causal relationship with this treatment.

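### Glaucoma other than known steroid response does not bar entry to a steroid-drop trial in which onset of glaucoma stops dosing: a minor, optional safety edit

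*Combined protocol and SAP*

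**What the plan says.** **Eligibility.** Section 6.2 of the protocol excludes "Known steroid-responder (steroid-response glaucoma"), and the synopsis excludes "Known steroid glaucoma responders". Neither list names any other glaucoma. The closest further item in section 6.2 is "Patient with ocular conditions potentially interfering with conjunctival or corneal grading", which is followed by an open list of examples that does not include glaucoma. Section 7.0 gives the acceptance rule: "Subjects meeting all the inclusion criteria and none of the exclusion criteria will be accepted into the study".

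**Product.** Section 2.3 states: "The combination is formulated as a 0.2% chlorhexidine 1% prednisolone acetate ophthalmic suspension". Under section 8.2 patients dose two-hourly during waking hours on the first day, then four times daily for four more days.

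**Stopping.** Section 6.4 states: "Subjects who experience onset of a corneal infiltrate, intraocular inflammation, or glaucoma are to receive rescue therapy". Study drug stops when rescue is given. Separately, section 6.3 lists as a ground for removal "Investigator decides it is in best interest of subject to withdraw from the study due to safety or efficacy issues". Section 10.6.4 requires the investigator to judge each adverse event and decide whether dosing goes on.

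**Monitoring.** The schedule of visits and section 10.3 both require tonometry at every visit.

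**The concern.** The protocol itself treats glaucoma as a hazard of this product. It keeps out known steroid responders, measures intraocular pressure as a safety outcome, and takes a patient off drug if glaucoma appears. It would be consistent with this not to start the drop in someone who already has glaucoma, and to have a stop rule that covers such a patient. As written, neither is assured. The entry criterion reaches only one subgroup, and the stop rule speaks of *onset*, which for a patient with existing glaucoma has already happened.

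What is at stake is the safety of an individual patient given a topical steroid. The comparison of SCH1 with vehicle is not at issue.

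**Working it through.** The plan gives no figure on this point, so the check is a reading of the provisions against each other.

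1. **Which exclusions could remove a patient with another glaucoma?** Section 6.2 has 10 exclusions and the synopsis has 7. One in each names glaucoma, and both are limited to known steroid response. These counts describe the lists and do not measure risk. The other candidates in section 6.2 are:
   - *Conditions that interfere with grading.* This removes some glaucoma patients, for example those with chronic injection after several operations or with pseudophakia. The test is interference with conjunctival or corneal grading, so a patient with quiet, medically treated glaucoma need not meet it.
   - *Chronic topical anti-inflammatory use.* This concerns anti-inflammatory drops, not pressure-lowering treatment.
   - *Investigator opinion.* This is tied to communication, compliance and return to visits, not to ocular safety.

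   No criterion removes glaucoma as such.

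2. **Can such a patient be randomised to the steroid?** Yes. Section 7.0 accepts anyone who meets the inclusion criteria and no exclusion, and section 5.1 allocates 1:1, so the chance of receiving SCH1 is one in two.

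3. **Does the mandatory stop cover that patient?** The trigger in section 6.4 is onset. Worsening is not named, and no pressure value is tied to entry or stopping.

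4. **Is there another route to stopping?** Yes. Section 10.6.1 defines an adverse event as "any untoward medical occurrence in a patient or clinical investigation subject administered a pharmaceutical product", which is wide enough to include worsening glaucoma. Section 10.6.4 then obliges the investigator to decide on continuation, and section 6.3 allows removal on safety grounds. What is missing is a named trigger.

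5. **Would worsening be looked for?** The schedule lists tonometry at 3 of 3 visits and section 10.3 agrees. The activity list in section 7.2 names it at Visit 1 only. That list is shorthand (it also leaves out the vital signs that the schedule requires), so the omission does not show that pressure would go unmeasured.

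6. **Cost in enrolment time.** About 30 patients (section 5.1) in twelve months (section 5.3) is 30 / 12 = 2.5 per month, so each replaced patient takes 12 / 30 = 0.4 month. The documents do not give the number to be replaced.

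7. **Effect on power.** None. The SAP calculation uses 15 per group, 20% against 80%, and Fisher's exact test at 0.05. Exact enumeration gives 87.2%, against the stated 87%. Neither the finding nor the fix changes any of these inputs.

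**The case against.** The strongest reply is that the sponsor identified the patients it judged to be at risk, known steroid responders, and excluded them. On this view, extending the exclusion to all glaucoma is a reviewer's preference that rests on clinical knowledge from outside the documents. The course is five days, pressure and slit-lamp findings are scheduled at every visit, the fundus is examined on Days 1 and 5, and the investigator must act on adverse events. The investigator's brochure and consent form, which may carry further guidance on risk, are not available to read. Most of this stands, and it sets the weight of the point. It does not remove the mismatch between the entry rule and the stop rule, which is visible from the protocol alone.

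Three stronger readings are tempting, and the documents support none of them:

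- *That patients with other glaucoma would be harmed.* Nothing in the documents shows that other glaucoma worsens over five days of this drop.
- *That a patient whose glaucoma worsens must stay on drug.* Sections 6.3 and 10.6.4 give a route off it, by judgement.
- *That pressure goes unchecked after Visit 1 because section 7.2 omits tonometry at Visits 2 and 3.* The schedule and section 10.3 require it. The omission is editorial and adds no weight here.

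It is also fair to say that the proposed wording leaves *worsening* to clinical judgement and sets no pressure limit. It adds a named trigger, not a numerical one.

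**Conclusion.** The point holds as a minor, optional-level improvement to patient safety. On the text, a patient with a known glaucoma other than steroid response, and not caught by the grading exclusion, may be randomised to a 1% prednisolone acetate drop and is not clearly covered by the mandatory stop rule. The number of such patients cannot be estimated, because the documents give no prevalence. The risk to each is limited by the short course, the scheduled pressure checks and the investigator's power to stop. There is no effect on bias, power or the analysis.

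The conclusion assumes that the listed criteria are complete and are applied as written, and that the documents not available add no further eligibility rule.

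**What to change.** - **Section 6.2 and synopsis:** keep the steroid-responder exclusion and add *Glaucoma of any type, by history or diagnosed at the Visit 1 examination*.
- **Section 6.4:** replace *glaucoma* with *onset or worsening of glaucoma*. Once the exclusion is in place, this serves only as a backstop for a case missed at Visit 1 or enrolled in error.
- **Section 7.2 (editorial only):** list tonometry under Visits 2 and 3 to match the schedule and section 10.3.

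No new procedure is needed: history, slit lamp, tonometry and fundus examination are already part of screening (section 7.1). The cost is a written amendment with IRB review (sections 16.0 and 17.0) and a few more screen failures, number unknown, at about 0.4 month of enrolment for each patient replaced.

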4.0 Endpoints

4.1 Primary Endpoints

The primary endpoint will be the achievement of a clinical cure defined as a rating of 0/3 for bulbar conjunctival injection and 0/3 for conjunctival exudates/discharge or clinical success defined as an overall decrease by 3 in the sum of both scores.

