7.2 Study Procedures/Assessments

The second visit has a +/- 1 day window. The third visit has a +/-1 day window.

Visit 1

Perform the following activities on Visit 1 (baseline)

- Review

- BCVA

- SLE and tonometry

- DFE

- Grading of injection / discharge

- Dispense study medication

Visit 2

Perform the following activities on Visit 2

- Record AEs

- Review of current medications

- Visual acuity

- SLE

- Grading of injection / discharge

Visit 3

Perform the following activities on Visit 3

- Record AEs

- Review of current medications

- Visual acuity

SLE
Grading of injection / discharge
DFE

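### The entry criteria exclude only chronic topical anti-inflammatory use, so patients who have already started other active eye drops for this episode are eligible, which can dilute the SCH1-versus-vehicle contrast

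*Combined protocol and SAP*

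**What the plan says.** - **Medication exclusion.** Section 6.2 excludes a "Patient taking topical anti-inflammatory drops on a chronic basis". The synopsis, under Eligibility Criteria, has "Patients taking topical anti-inflammatory medications on a chronic basis". The two agree, and no other criterion concerns prior or current eye drops. The section 6.2 exclusion for conditions that interfere with grading is about the eye itself and does not cover medication.
- **Time before entry.** Section 6.1 requires "Onset of symptoms in most recently affected eye less than 72 hours prior to visit".
- **Acceptance.** Section 7.0: "Subjects meeting all the inclusion criteria and none of the exclusion criteria will be accepted into the study".
- **After entry.** Section 7.2 lists "Review of current medications" at Visits 2 and 3, and the synopsis schedule marks current medications at all three visits. No washout or list of restricted eye drops is given. Non-study drops are not a withdrawal reason in section 6.3. The nearest item there is discretionary: "Investigator decides it is in best interest of subject to withdraw from the study due to safety or efficacy issues". Rescue in section 6.4 is tied to corneal infiltrate, intraocular inflammation or glaucoma.
- **Outcome and analysis.** Section 4.1 requires "a rating of 0/3 for bulbar conjunctival injection and 0/3 for conjunctival exudates/discharge", or a fall of 3 in the summed grades. The synopsis specifies intent-to-treat for all patients. Neither it nor the SAP mentions patients who use other eye drops.

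**The concern.** The comparison is meant to isolate SCH1 against its vehicle. The protocol itself treats other eye drops as able to alter the disease. Section 2.1 says antibiotic/anti-inflammatory combinations have been useful in routine bacterial cases and can prolong or worsen viral ones. Section 2.3 gives prednisolone acetate as one of SCH1's two active ingredients. A vehicle patient on a short course of steroid drops could therefore be receiving part of the test product, and the exclusion, limited to chronic use, would not keep that patient out.

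Three results could be affected:

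- **The Day 5 grades.** If other drops help vehicle patients, the vehicle cure rate rises and the difference shrinks.
- **The baseline grades.** A patient whose signs are already reduced to 1 + 1 = 2 cannot fall by 3, so only the 0/0 route to the endpoint remains.
- **Microbiological cure.** The synopsis analyses elimination of the pre-treatment pathogen, which earlier anti-infective drops could influence.

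An entry rule cannot be repaired at the analysis stage. With 15 patients per arm there is little room to absorb a smaller contrast.

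**Working it through.** **Inputs from the documents.** The SAP sample-size section gives day 5 clinical cure rates of 20% (placebo) and 80% (SCH-1), 15 patients per group, Fisher's exact test at 0.05 and 87% power. The SAP also states that P-values are two-sided. The synopsis agrees on 15 per arm. Section 11.0 speaks of 30 in each group, a separate inconsistency; the SAP figure is used here.

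**Step 1: reproduce the plan's figure.** Power = sum of Bin(x; 15, p_V) × Bin(y; 15, p_S) over all 16 × 16 outcomes (x, y) whose two-sided Fisher P-value is at most 0.05. With p_V = 0.20 and p_S = 0.80 this gives 87.2%, which matches the stated 87%.

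**Step 2: dilution.** Assumptions, none of them in the documents: a share f of vehicle patients uses other active drops, those patients are cured at rate r, and the SCH1 rate stays at 80%. Then

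p_V = 0.20 × (1 − f) + r × f.

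For example, f = 0.2 and r = 0.5 give 0.16 + 0.10 = 0.26.

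| r | f = 10% | f = 20% | f = 30% |
|---|---|---|---|
| 40% | p_V 22%, power 84% | 24%, 80% | 26%, 77% |
| 50% | 23%, 82% | 26%, 77% | 29%, 70% |
| 80% (worst case) | 26%, 77% | 32%, 63% | 38%, 49% |

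The true difference falls from 60 points to between 58 (80 − 22) and 42 (80 − 38).

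**Step 3: would scoring every user as not cured be a better primary rule?** Two cases, using the same f:

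- Equal use in both arms: the rates become 0.20 × (1 − f) and 0.80 × (1 − f), that is 18% v 72%, 16% v 64% and 14% v 56%. Power is 77%, 65% and 53%, so the loss is substantial.
- Use only in the vehicle arm: the vehicle rate falls to 18%, 16% and 14% against 80%. Power rises to 90.1%, 92.5% and 94.5%, because the rule itself enlarges the contrast in favour of SCH1.

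As a primary rule it can therefore cost power or favour the drug, depending on who uses the drops.

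**The case against.** The strongest reply has five parts.

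1. **Silence is not permission.** A reader might infer that patients may carry on with their own drops during the trial. No section says so; the plan is silent. What stands is narrower: under section 7.0, a patient who has already started such drops is eligible.
2. **Use is recorded.** A reader of section 7.2 alone might think medications are captured only at Visits 2 and 3. The synopsis schedule also marks them at Visit 1, so use at entry can be described by arm. That helps reporting but does not change who is enrolled.
3. **Randomisation and masking protect the comparison.** A reader might infer a biased result. Use before randomisation is balanced in expectation. If 6 of 30 patients were users, a 5–1 or 6–0 split would occur with probability 17% under a simple 15/15 allocation, but that is chance variation already covered by the test's type I error. Heavier use during the study by vehicle patients who are not improving is plausible, but nothing in the documents supports or sizes it over five days. This objection stands, and dilution is what remains.
4. **The effect of other drops may be modest.** Section 2.1 calls adenovirus the more common cause, and section 2.4 says no current treatment handles both viruses and bacteria. The 80% row gives any other drop the full cure rate assumed for SCH1, so the 49% figure is an extreme and should not be read as an expectation.
5. **Intent-to-treat already implies an answer.** Read plainly, the observed Day 5 grade counts whatever else was used. That is a defensible primary analysis. Counting users as failures answers a different question, and Step 3 shows its drawbacks.

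**Conclusion.** The concern holds as a gap in eligibility with a dilution effect. It is a design weakness, not a contradiction: section 6.2 and the synopsis agree, and both cover only chronic topical anti-inflammatory use. Patients already treated for this episode with other active drops, including one of SCH1's own active ingredients, can be randomised and scored on signs those drops may change.

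Under the assumed values, power falls from 87% to between 84% and 70% when users respond at 40% to 50%, and to 49% at the worst-case corner. The share of users, their response and the unchanged 80% SCH1 rate are all assumptions; the documents give no figure for the first two. The documents do not support a claim of directional bias from pre-randomisation use, nor a claim that continued use is allowed. The change is worth making because it is cheap and cannot be made after enrolment.

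**What to change.** **Eligibility (section 6.2 and synopsis).** Keep the exclusion of chronic topical anti-inflammatory use, and extend it to topical ocular anti-infective, anti-inflammatory, antihistamine or vasoconstrictor drops used for the current episode before randomisation. The exact class list is for the sponsor. This is an entry criterion and does not direct how patients are treated.

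**Analysis (SAP).** Keep intent-to-treat on observed grades as primary, and state that this applies whatever non-study eye drops were used. Report non-study eye-drop use by arm from the current-medications record at Visits 1 to 3. Prespecify one sensitivity analysis that counts patients who used such drops after randomisation and before the Visit 3 grading as not cured, and read it with Step 3 in mind.

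**Cost.** Accrual may be slightly slower because some patients who have already started drops are lost, and there is one extra analysis. No new data are collected.
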